Ventilation-related measurements do not adequately reflect the DNR in COPD patients, because their alterations in respiratory mechanics modify the relationship between the DNR and inspiratory flow. Nor can it be related to variables relating to respiratory system pressures, because these vary according to the contractile capacity of the respiratory muscles and their tension, properties that are independent of the DNR, especially in the presence of pulmonary hyperinflation (Cherniack and Snidal 1956).

But recently the measurement of diaphragmatic contraction using an oesophageal probe with electrodes, diaphragmatic electromyography (EMGdi) (Sinderby, Spahija et al. 2001, Spahija, de Marchie et al. 2010, Reilly, Ward et al. 2011) This has allowed the precise quantification of DNR, since a measure is obtained that is, from a neurophysiological point of view, closer to the generation of the respiratory impulse than changes in pleural pressure (Luo, He et al. 2014). The measurement of DNR by EMGdi has demonstrated a close relationship between the increase in dyspnea, measured by the Borg scale, and DNR. The measurement of the respiratory minute volume is poorly related to dyspnea because under physical effort, and once the decoupling point is exceeded, despite the compensatory increase in respiratory rate and muscle effort and respiratory drive, the minute volume reaches a plateau. Despite the parallel increase in dyspnoea and neural drive, no increase in minute volume is obtained (Jolley, Luo et al. 2015).

The study of DNR behaviour, as described above, has been conducted in patients with severe COPD at rest and during physical exercise (Jolley, Luo et al. 2015), but has not been studied in patients with WV. It is possible that WV, by increasing alveolar ventilation and tidal volume, may modify the respiratory mechanical characteristics responsible for VN, and we have therefore set out to investigate the behavior of VN in patients with COPD and WV at baseline and during exercise.

The measurement of the neural drive from diaphragmatic electromyography is considered the "gold standard" method but has a number of associated problems. Perhaps the most relevant is the invasiveness of the method: it

requires the use of an esophageal probe with multiple electrodes, whose insertion may be uncomfortable for the patient.

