The study protocol has been approved by the Research Ethics Committee of the CEIC of the Hospital 12 de Octubre (resolution 18/025). Attached is informed consent. Participation in this study is completely voluntary, and does not affect the assessment of the patient on the transplant waiting list. From the point of view of confidentiality, compliance with the provisions of the LOPD 1.5/1999 will be ensured. Specifically, a database will be generated with a consecutive number as the only data identifying the patient. The correlation between the number of inclusion in the study and the number of the clinical history (as a unique identifier) will be stored in a database located in the folder of the Pneumology service in the "Y" server, with access protected by a password, only authorized to the two investigators of the work ([name] and [name]).

The intervention on the patients does not pose any risk (derived from the determination of surface electromyography) and only consists of the measurement of muscle activity during basal effort, with NIV and with high-flow nasal glasses, in a similar way to how rehabilitation of these patients is currently carried out, and within the usual rehabilitation program.

Studio design

Experimental, longitudinal, prospective and controlled study, with a branch and comparison before/after the same individuals.

Variables and measurements

First visit, baseline situation (coinciding with scheduled review in ventilation or transplant consultation or rehabilitation):

Medical history: smoking history (packet)

Anthropometric variables: age, weight, height, BMI.

Functional variables: BODE, BODEx, FEV1 (%), FVC (%), VR, TLC, DLCO, DLCO/VA Basal arterial blood gas and basal mean tcpCO2.

Clinical variables: measurement of dyspnea using Borg and MRC scales.

Checking inclusion/exclusion criteria and signing IC

The usual pre-transplant respiratory rehabilitation program includes 24 sessions, with a frequency of 2 sessions per week, in which it is performed:

- Warm-up exercises, elongations of spine, thorax and shoulder girdle.
- Respiratory physiotherapy exercises.
- Upper limb strengthening with progressive weight dumbbells (80% of 1RP 3 sets of 15 repetitions for biceps, triceps and deltoid)

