- Neuro-respiratory coupling: NVU: $\text{EMGDimax\%}/\text{Vt}$. To determine the neurorespiratory coupling (NVU variable) the peak value (above the baseline) of the maximum muscular activity (averaged by square root of the EMG value in mV) both diaphragmatic (EMGDimax) and parasternal (EMGparamax) in the maneuvers of maximum voluntary ventilation and maximum inspiratory pressure (MIP) will be taken. On that value, taken as 100%, the average value of EMGpara and standardized EMGdi (RMS) in each ventilatory situation (spontaneous or low NIV ventilation) will be calculated. At each point of effort (in each minute of the exercise protocol) the ratio between the standardized EMG value (parasternal and diaphragmatic) and the tidal volume (obtained by integration of the flow signal by means of a pneumotachograph connected to the MV-in NIV circuit or an oronasal airtight mask-in Vesp) shall be measured. To facilitate the interpretation of the exhaled VC, a non-leak mask with the intentional leak connected to the circuit shall be used before the pneumotachograph.
- The degree of dyspnea will be determined with a Borg and Analog-Visual scale at 60" of effort
- The entire effort protocol will be monitored by TCP CO_2

- Total pedaling time and number of stops will be collected.
- At the end of this second visit, after about 20 minutes of rest, an exercise of about 10 minutes at constant load will be started to adjust the NIV parameters.
 - Based on the previously titrated home parameters, the inspiratory trigger is adjusted and EPAP is progressively increased until ineffective efforts are eliminated and trigger delay is minimized, and support (IPAP) is increased until a subjective decrease of at least 20% in the mean RMS value is achieved or until patient tolerance limits it.

Third visit, exercise with non-invasive mechanical ventilation:

- Effort protocol: it will be done in a similar way to the one done in spontaneous ventilation with similar calculations and measurements.
- In this third visit, exercise will be performed under non-invasive ventilation
- Ventilator programming: the parameters set in visit 2 will be used, recording the changes made with respect to the previous home programming.
- It will be performed at the same load in W as the test in spontaneous ventilation, maintaining a constant pedaling frequency between 35 and 40 cpm.
- They will be collected as other variables:
 - Rate of asynchronies during effort and % of ineffective effort

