 - Neuro-respiratory coupling: NVU: EMGDimax%/Vt
 - Borg in times of 60" effort
 - TcpCO₂ final

- ETCO₂ final effort
- Number of stops and total pedalling time.

Fourth visit, exercise with high flow oxygen therapy:

Within the rehabilitation program, and as with mechanical ventilation, the patient will be offered exercise under high flow oxygen therapy, at constant flows of 50lpm and with FiO₂ adjusted according to SPO₂, to obtain a constant saturation between 92 and 94%. The same load and pedaling frequency will be maintained, with similar variables collected.

In summary, the included subject is scheduled for 4 study related visits: baseline, exercise level determination, spontaneous exercise, NIV exercise and high flow exercise. These visits fall within the normal care process of the pre-transplant rehabilitation program, not requiring additional patient visits for the study. The only difference with the care process is that neurorespiratory coupling (EMG for and exhaled flow) will be measured during exercise. The exercise program is the same that would have to be performed during conventional rehabilitation. Currently, the use of NIV or high flow during rehabilitation is routine, but the objective is to measure the physiological effect of rehabilitation, in a non-invasive way.

Statistical analysis

The statistical program SPSS 22.0 will be used for the analysis of the variables studied, to estimate the measures of centralization and dispersion of the results of the tests carried out and for multivariate analysis and correlations between the variables.

The NVU variable will be compared by means of a single-factor ANOVA with repeated measurements between the spontaneous and non-invasive ventilation determinations.

A difference of more than 20% is expected to be found in this value. It will be considered significant if $p < 0.05$.

The remaining secondary variables will be compared by t for repeated samples once their normal distribution has been confirmed.

Sample size calculation:

According to previously published work (Jolley, Luo et al. 2015), all COPD patients expressed neuro-respiratory decoupling. Assuming a 10% decrease in NVU as clinically significant, with a 95% confidence level (alpha 5% error) and a power of 80% (1-beta), assuming 5% losses, a required number of 18 patients is calculated. The sample size calculator for ANOVA provided by <http://powerandsamplesize.com/> has been used.

Potential limitations

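### The main endpoint, NVU, is defined on diaphragmatic EMG while the protocol describes surface, non-invasive recording, and the ratio to be tested is not named

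*Combined protocol and SAP*

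**What the plan says.** No variable is labelled as the primary endpoint, but NVU has that role. It measures what the main objective is about, it is the variable in the main test, and the sample size of 18 rests on a 10% decrease in it.

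On the signal, the protocol says:

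- **Variables and measurements, spontaneous-ventilation and NIV exercise visits.** The formula, given at both, is "Neuro-respiratory coupling: NVU: EMGDimax%/Vt".
- **Same section, definition of NVU.** The 100% reference is the maximal activity, "both diaphragmatic (EMGDimax) and parasternal (EMGparamax"), in two manoeuvres (maximum voluntary ventilation and MIP). At each minute the plan then measures "the ratio between the standardized EMG value (parasternal and diaphragmatic) and the tidal volume".
- **Background.** EMGdi is introduced as "measurement of diaphragmatic contraction using an oesophageal probe with electrodes, diaphragmatic electromyography (EMGdi"), and the method "requires the use of an esophageal probe with multiple electrodes, whose insertion may be uncomfortable for the patient".
- **Ethical aspects.** "The intervention on the patients does not pose any risk (derived from the determination of surface electromyography").
- **Visit summary, after the fourth visit.** The only departure from usual care is that "neurorespiratory coupling (EMG for and exhaled flow) will be measured during exercise"; the stray word is probably a mistranslated *para* (parasternal). It adds that "the objective is to measure the physiological effect of rehabilitation, in a non-invasive way".
- **Potential limitations.** EMG is discussed as a surrogate for EMGdi, with a recumbent bicycle to limit parasternal interference.
- **Statistical analysis.** One repeated-measures ANOVA compares NVU between spontaneous and non-invasive ventilation, at p<0.05.

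On the construct, the operational hypothesis is about a gap between neural drive and minute volume. The statistical hypotheses H0 and H1 are written in NVU.

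**The concern.** A reader of the eventual result must know which muscle the p-value concerns. The formula gives one answer, the description of the recording points to another, and the definition mentions both. The protocol does not treat the signals as interchangeable: the Background calls parasternal EMG during exercise controversial. If both signals exist when the analysis is run, the analyst can choose between two ratios after seeing them.

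The second issue is interpretive. A fall in EMG% per unit of tidal volume might be reported as better drive relative to minute volume, as the operational hypothesis puts it, without that having been shown.

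**Working it through.** **1. The passages side by side**

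| Reading | Agrees with | Conflicts with |
|---|---|---|
| NVU is diaphragmatic, by oesophageal probe | Formula at both visits; Background | Surface EMG in Ethical aspects; non-invasive visit summary; no visit places a catheter |
| NVU is parasternal, by surface EMG | Ethical aspects; visit summary; Potential limitations | Formula at both visits; the two-signal definition |
| Both ratios are recorded | Definition of NVU | A single NVU in the ANOVA; surface-only description |

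No reading fits every passage, so each needs a text correction.

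**2. Type I error if both ratios exist**

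Inputs: alpha 0.05 (Statistical analysis); no adjustment for two ratios stated. The correlation between the ratios is not given and is assumed.

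- Either two-sided result counts: perfectly correlated ratios give 5%; independent ratios give 1 − 0.95² = 9.75%. Simulated pairs of correlated paired t tests with 17 patients give 9.1% at correlation 0.5, 7.9% at 0.8 and about 7% at 0.9.
- Only a significant fall counts (0.025 in that tail): 2.5% to 1 − 0.975² = 4.9%.

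The plan does not settle which success rule applies. H1 says in words that decoupling is less with NIV, its formula has NVU greater with NIV, and the sides of the test are not stated.

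**3. The plan's own sample size**

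N = 18 cannot be reproduced, because no SD is given. Working backwards, 17 evaluable patients with 5% losses gives 17/0.95 = 17.9, rounded up to 18. For 80% power to detect a 10% change with a two-sided paired t test, 17 patients imply an SD of differences of 13.8 percentage points (standardised effect 10/13.8, about 0.72). The text does not say which EMG signal the SD belongs to.

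**4. Tidal volume against minute volume**

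Since VE = Vt × rate, EMG%/Vt = (EMG%/VE) × rate. Assume, for illustration only, a start of Vt 1.0 L, rate 30/min and VE 30 L/min, with VE unchanged and EMG% a mean over the minute. For a fractional fall e in EMG%, NVU changes by (1 − e) × rate/30 − 1, and EMG%/VE changes by −e.

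| Fall in EMG% | Rate | Change in NVU | Change in EMG%/VE |
|---|---|---|---|
| 0% | 27 | −10% | 0% |
| 5% | 27 | 0.95 × 0.9 − 1 = −14.5% | −5% |
| 20% | 27 | 0.80 × 0.9 − 1 = −28% | −20% |
| 20% | 33 | 0.80 × 1.1 − 1 = −12% | −20% |

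In the second row the two ratios fall on opposite sides of the plan's 10% mark. If EMG% is instead a per-breath level, drive per minute is EMG% × rate, and (EMG% × rate)/VE = EMG%/Vt. Rate cancels and NVU is consistent with the hypothesis.

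**5. What the definition leaves open**

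The text gives mV, RMS, scaling to 100% of maximum, an average per condition and a ratio per minute. It does not say whether EMG% is a per-breath level or a per-minute mean, which of the two manoeuvres sets 100%, or which value per condition enters the ANOVA.

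**The case against.** The strongest reply is that parasternal surface EMG is plainly intended and the formula carries a wrong label. The oesophageal probe appears as background, where its invasiveness is named as a drawback. No visit places a catheter, the budget itemises none, and the recumbent bicycle addresses parasternal interference. Much of this stands, and it is probably the likeliest reading. It still leaves the formula wrong in two places and the two-signal definition unexplained. The opposite reply, that NVU is diaphragmatic and the parasternal ratio supportive, is nowhere stated and conflicts with the surface, non-invasive text. A surface recording of the diaphragm is conceivable but not described.

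A reader might infer more than the documents support:

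- *That two ratios feed one test and the error rate is inflated.* The definition reads as computing both ratios, but no section says that both enter the test or that either may win. If one signal is recorded, the error figures do not apply.
- *That the ethics committee or patients were misinformed.* Ethical aspects is protocol text, not the submission, and the consent pages are not available here.
- *That the EMG measure is undefined.* Most of it is specified; the open items are those in step 5 of the working.
- *That the trial tests the wrong hypothesis.* H0 and H1 are stated in NVU, and tidal volume is a per-breath quantity, so a per-breath EMG% is at least as natural. The NIV adjustment also aims at a fall of at least 20% in mean RMS unless tolerance limits it, which makes a wholly rate-driven fall in NVU less likely.

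**Conclusion.** The contradiction on the EMG signal holds and should be corrected, because NVU carries the main objective, the main test and the sample size. It rests on the text alone and depends on no assumed figure.

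The possible inflation of type I error is conditional and moderate. It requires both signals to be recorded and either result to count, and its size depends on an unstated success rule and correlation. The more certain harm is that the p-value cannot be tied to a named signal.

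The mismatch between minute volume and tidal volume is minor. It matters only if EMG% is a per-minute mean, and the percentages shown for it rest on assumed rates and volumes. They show that the two ratios can diverge, not that they will in this trial.

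**What to change.** 1. Name one recorded EMG signal as primary and say how it is recorded. Correct the NVU formula at both visits to match, and label any other signal supportive. Reconcile the Background, Ethical aspects, the definition of NVU, the visit summary and Potential limitations with that choice.
2. State whether EMG% is a per-breath level or a per-minute mean, which manoeuvre sets 100%, and which single value per condition enters the ANOVA.
3. Reword the operational hypothesis and the conclusion as the ratio tested. Report respiratory rate and VE by condition from the flow already recorded. If EMG% is a per-minute mean, make no minute-volume claim unless EMG%/VE also falls.

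This is rewording plus analysis of existing recordings; no new measurement is needed. The conclusion becomes narrower. If the primary signal is parasternal, the unstated SD behind N = 18 must be confirmed for that signal or the stated power qualified.

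Keeping both ratios as alternative routes to success would cost more. At alpha 0.05/2 = 0.025 each, and with the back-solved effect of about 0.72, power at 17 evaluable patients falls from 80% to 69%. Restoring 80% needs 21 evaluable, or 21/0.95 = 22.1, rounded up to 23 with losses.
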